## **CIPN measurements**

### ***Pediatric chemotherapy-induced peripheral neuropathy (P-CIN)***

It was originally developed for children  $\geq$  6 years old who had received or were receiving neurotoxic chemotherapy and reported peripheral neuropathy to quantify numbness and tingling in the hands and feet and the functional deficits in the past two to three days[6]. The P-CIN comprises 13 items, with eight items to rate CIPN symptoms in the hands and feet and five items to rate the difficulty of performing functional tasks, e.g., standing on one leg and closing eyes for 15 seconds[6]. Each item is rated using a 6-point faces scale. The total score ranges from 0 to 65 with higher scores indicating more severe CIPN[6].

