### ***Psychometric evaluation***

#### ***Reliability assessment***

Reliability refers to the ability of a instrument to determine that a measurement yields reproducible and consistent results. Three important reliability criteria are: internal consistency, and stability. **Internal consistency** shows if all subparts of an instrument measure the same characteristic. Cronbach's alpha coefficient and the corrected item-total correlation will be used to assess internal consistency of the P-CIN. **Stability** estimates the consistency of measurement repetition and can be performed using test-retest method. The time span between measurements will influence the interpretation of test-retest reliability; therefore, the time span from 10 to 14 days is considered adequate for the test and retest. A group of 50 children will be randomly selected for the achievement of statistical significance for an alpha value is 0.05 and with a power of 0.90.[22] The intraclass correlation coefficient (ICC) is one of the most used tests to estimate continuous variables stability, as it takes into

account the measurement errors.

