### ***Factor analysis***

Factor analysis is valuable for evaluating sampling adequacy, internal consistency, factor rotation, factor identification, item retention, and other analytical processes. Exploratory Factor Analysis (EFA) and Confirmatory Factor Analysis (CFA) are two common techniques used in scale adaptation studies. EFA will be conducted to determine the number of underling latent factors and the structure of items. Following the execution of the EFA, a measurement model will be applied to examine CFA using three critical results: parameter estimates, fit indices, and modification indices. In our study, the sample will be randomly

split into two halves (half for EFA and half for CFA).

EFA will be performed by using the SPSS software, version 29.0 for Mac (SPSS Inc., Chicago, IL, United States). Suitability of the matrix for conducting the EFA will test using the Kaiser-Meyer-Olkin (KMO) test and Bartlett's test of sphericity. The KMO sampling adequacy test will be deemed adequate if the value was greater than 0.6. A significant level of  $P$ -value  $< 0.05$  of Bartlett's Test of Sphericity indicates EFA can be performed. The number of factors that should be retained in the model was determined using eigenvalues and scree-plot. All factors with eigenvalues above one was retained according to the Kaiser's criteria. In addition, factors corresponding to data points lying above the point of inflexion of the scree-plot were also retained. Principal component analysis will be performed to conduct an additional factor analysis, which helps determine the loadings for every factor selected. Analyze the factor composition and the factor loading of each item on the corresponding factor, and delete items with factor loading  $< 0.50$ . Cumulative variance contribution rate be above 50%. We will apply the varimax type of rotation. In addition, varimax rotation will be chosen since it minimizes factor complexity while, at the same time, maximizing the variance of factor loadings.

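### Varimax forces the EFA factors to be uncorrelated, although the 13 items are used as one severity construct; if the factors correlate, it does not give the simple structure for which it was chosen

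*Protocol*

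**What the plan says.** The Factor analysis section of the Protocol is definite about rotation: "We will apply the varimax type of rotation". The reason given is that "varimax rotation will be chosen since it minimizes factor complexity while, at the same time, maximizing the variance of factor loadings". It does not argue that the P-CIN domains are independent. Loadings come from principal components: "Principal component analysis will be performed to conduct an additional factor analysis, which helps determine the loadings for every factor selected". Items with a loading below 0.50 on their corresponding factor are deleted.

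Other sections treat the instrument as a single construct:

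- **P-CIN description:** "The P-CIN comprises 13 items, with eight items to rate CIPN symptoms in the hands and feet and five items to rate the difficulty" of functional tasks, and "The total score ranges from 0 to 65 with higher scores indicating more severe CIPN".
- **Reliability assessment:** internal consistency "shows if all subparts of an instrument measure the same characteristic", to be judged by Cronbach's alpha and corrected item-total correlations.
- **Validity assessment:** the P-CIN is set against one CIPN diagnosis, with a ROC curve and an optimal cut-off by the Youden statistic.

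A CFA in Amos follows on the other half of the sample. Parameter estimates are among the results to be examined. The text does not say whether the CFA factors may covary.

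**The concern.** If symptom and function items are both expressions of the same neuropathy, which is the reading under which one sum, one alpha and one cut-off make sense, the factors behind them should be positively correlated. Varimax keeps its axes at right angles whatever the data show. When the item clusters lie closer than a right angle, orthogonal axes cannot pass through both. Each cluster then sits off its axis, and every item shows a loading on the factor to which it does not belong. The stated aim, low factor complexity, is what suffers.

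At stake is the factor structure that will be reported for the Chinese version. A reader could see cross-loadings produced by the rotation alone, and would not learn from the EFA how strongly the symptom and function domains are related.

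**Working it through.** **Inputs from the Protocol.** There are 8 + 5 = 13 items, and "Each item is rated using a 6-point faces scale". Scored 0-5, the maximum is 13 × 5 = 65, which reproduces the stated score range. The sample of 300 is split in half, so the EFA has 300 / 2 = 150 children.

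**Assumptions, not in the Protocol.** Two factors (8 symptom items, 5 function items), equal loadings λ of 0.6, 0.7 or 0.8, zero true cross-loadings, a factor correlation φ from 0 to 0.8, and continuous normal items.

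**Step 1: component loadings.** With equal loadings within a block, the first two components span the two block composites. An item's loading on its own composite is

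- symptom: a = √[(1 + 7λ²)/8]
- function: b = √[(1 + 4λ²)/5]

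The correlation between the composites is r = φλ²/(ab).

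- λ = 0.6: a = √(3.52/8) = 0.663, b = √(2.44/5) = 0.699, r = 0.36φ/(0.663 × 0.699) = 0.777φ
- λ = 0.7: a = √(4.43/8) = 0.744, b = √(2.96/5) = 0.769, r = 0.49φ/(0.744 × 0.769) = 0.856φ
- λ = 0.8: a = √(5.48/8) = 0.828, b = √(3.56/5) = 0.844, r = 0.64φ/(0.828 × 0.844) = 0.916φ

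**Step 2: varimax.** Kaiser-normalised varimax places the right-angled axes symmetrically about the two clusters, so each cluster lies δ = ½ arcsin(r) off its axis. The main loading is a cos δ (or b cos δ) and the cross-loading is a sin δ (or b sin δ).

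Worked case, λ = 0.7 and φ = 0.7: r = 0.856 × 0.7 = 0.599; δ = ½ arcsin(0.599) = 18.4°; sin δ = 0.316. Cross-loadings are 0.744 × 0.316 = 0.23 (symptom) and 0.769 × 0.316 = 0.24 (function). Main loadings are 0.744 × cos 18.4° = 0.71 and 0.769 × cos 18.4° = 0.73.

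**Step 3: the range.** A numerical search over the rotation angle gives the same values as this formula.

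| Factor correlation φ | Cross-loading, λ = 0.6 to 0.8 |
|---|---|
| 0 | 0.00 |
| 0.3 | 0.08-0.12 |
| 0.5 | 0.13-0.20 |
| 0.7 | 0.19-0.29 |
| 0.8 | 0.22-0.34 |

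With the same components, an oblique rotation can put an axis through each cluster. Cross-loadings are then 0.00, and r is estimated rather than fixed at zero.

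**Step 4: does rotation apply?** Under the eigenvalue-above-one rule it does in this model. The second population eigenvalue is 1.30-1.53 at φ = 0.7 and 1.08-1.14 at φ = 0.8, so two factors are kept.

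**Step 5: samples of 150 under varimax.** With loadings of 0.6-0.7, cross-loadings above 0.30 occur for about 3-4% of items at φ = 0.5 and 17-22% at φ = 0.7. The 0.30 mark is only a yardstick; the Protocol has no cross-loading rule. Up to φ = 0.7, the share of items with a main loading below 0.50 is at most about 5% (at λ = 0.6 and φ = 0.7). The share of items whose largest loading is on the wrong factor is 0-1.4% at φ = 0.7 and at most about 6% at φ = 0.8, the latter with loadings of 0.6.

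**The case against.** The case for leaving the plan alone has real content. Varimax is a choice of axes and does not assert that the domains are independent, and nowhere does the Protocol say that the factors correlate. Rotation leaves the number of factors, the communalities and the cumulative variance unchanged. Unless different items are deleted, the total score, alpha, ICC and ROC analysis come out the same. The size of the effect rests on a correlation that nobody has yet measured. All of this stands and limits the point to the EFA loadings and how they are read.

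Three stronger conclusions may be tempting, and the Protocol does not support them.

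- **That the factor correlation is never estimated.** This is true of the EFA only. The CFA reports parameter estimates, and nothing in the text fixes factor covariances at zero. A detail that may sit in an analysis plan not at hand is no finding.
- **That item assignment to factors becomes arbitrary.** It does not. About 1% of items at most are misplaced at a correlation of 0.7, and the 0.50 deletion rule is barely affected except with weak loadings.
- **That the evidence for the total score is lost.** Alpha, item-total correlations, the unrotated eigenvalues with the scree plot, and the CFA all bear on it and remain.

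What the objection does not answer is that the only reason given for varimax is simple structure, and that this reason fails when the factors correlate.

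**Conclusion.** The point holds as an improvement to the EFA, not as a flaw that undermines the validation. The chosen rotation does not fit the Protocol's use of the 13 items as one severity construct, and its stated justification does not hold for correlated factors. Under the assumed two-factor model, varimax alone produces cross-loadings of about 0.13-0.20 at a factor correlation of 0.5, 0.19-0.29 at 0.7 and 0.22-0.34 at 0.8, where the true value is zero, and the EFA reports no factor correlation.

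These sizes depend on the assumed loadings and above all on the assumed correlation. At 0.3 the cross-loadings are only 0.08-0.12, and if a single factor is retained there is nothing to rotate.

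**What to change.** In the Factor analysis section, replace varimax with an oblique rotation (direct oblimin or promax, both in SPSS). Report the pattern loadings and the factor correlation matrix, and apply the 0.50 deletion rule to the pattern loadings. Keep varimax only if the factor correlations prove negligible; in that case the two solutions essentially agree. It would help to add one sentence saying that factors are free to covary in the CFA.

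If principal components are kept for extraction, the reported correlation is between components and is lower than the factor correlation: 0.78 to 0.92 of it for loadings of 0.6 to 0.8, by the formula above. The text should say so.

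The change costs one menu option and needs no further data and no further burden on the children. The downside is that in a sample of 150 an item's pattern loading can be a little lower than its varimax loading. Somewhat more items may therefore fall below 0.50 when loadings are weak.

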### ***Feasibility***

Feasibility means percentage of children who completed the P-CIN independently. In this study, we use the item 'Did the children need assistance by a parent or other adults to complete the survey?' to evaluate the feasibility.

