### **Data collection**

Research team contacts with the dean of Nursing Department of each site. After approval, the name list of pediatric oncology patients receiving the neurotoxicity agents will be provided. Well-trained registered nurses will identify potentially eligible participants through checking the medical records and confirm the eligibility based on the inclusion and exclusion criteria. In addition, the registered nurse will approach these potential participants and ask all children and their parents who accompanied children for hospitalization in inpatient clinic or medical consultation in the outpatient clinic, and introduce the study. The information sheet including research purpose, procedures, confidentiality measures, and their rights as participants will be provided. All pediatric patients agree to participate the study will invite to sign an informed consent form with their legal guardian in accordance with the Declaration of Helsinki. We assure participants’ responses would remain confidential. After obtaining written consent, each child will be asked to complete the questionnaire independently. For those children who are unable to self-report, parents will

be asked to assist them in completing the questionnaire. To assess test-retest reliability, a sample of 50 children will be randomly selected to respond by phone to the P-CIN 2 weeks later.

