## **Sample size**

Although there is no golden standard for the sample size calculation for validation study in nursing research, the recommended sample size for factor analyses is between 150 to 180.[7] In addition, the Exploratory Factor Analysis (EFA) and Confirmatory Factor Analysis (CFA) must be conducted on different datasets.[8] We therefore determined to recruit 300 pediatric oncology patients in our validation study.

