### ***Chinese version of the Pediatric Quality of Life Inventory (PedsQL) Cancer Module***

The PedsQL Cancer Module will be used to assess the participants' QoL. This scale contains 27 items grouping into eight subscales including (1) pain and hurt, (2) nausea, (3) procedural anxiety, (4) treatment anxiety, (5) worry, (6) cognitive problems, (7) perceived physical appearance, and (8) communication. There are parallel and identical versions for pediatric patients (young child: 5-7 years old, child: 8-12 years old, and adolescent: 13-18 years old) and parents (toddler: 2-4 years old plus the above three age groups). The participants rated how frequently a particular problem occurred in the past month, using a three-point Likert scale (0 = Never, 2 = Sometimes, 4 = Almost always) for children 5-7 years old and a five-point Likert scale (0 = Never, 1=Almost never, 2=sometimes, 3=often, 4 = Almost always) for children of 8-18 years old and for the parents of patients of all ages. Each item score will be reversely scored and then linearly transformed into 0-100 scale (0 = 100, 1 = 75, 2 = 50, 3 = 25, 4 = 0). The scale is the average of the total item scores. Higher scores represent better quality of life (QoL). The psychometric properties of the Chinese version of the scale have been well-examined[21]. This scale has been demonstrated as a valid and reliable tool in assessing QoL for Hong Kong Chinese adolescent with cancer[21].

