good discrimination, 0.4 and above indicate very good discrimination. Good internal consistency reliability is indicated by a Cronbach's alpha coefficient  $\geq 0.70$  and item-total score correlations ranging from 0.30 to 0.70. The intraclass correlation coefficient (ICC) will be used to evaluate the **test-retest reliability**. For the results interpretation, minimum ICC values of 0.70 are considered satisfactory, values above 0.8 or 0.9 are often regarded as a sign of good or excellent test-retest reliability.[26] Concerning for the **content validity**, a scale with excellent content validity should be composed of I-CVIs of 0.78 or higher and UA -CVI/Ave-CVI of 0.8 and 0.9 or higher, respectively. Spearman's correlation coefficient ( $r$ ) will be performed to evaluate **convergent validity**. The correlation values for convergent validity are classified as follows:  $r=0$ , no correlation;  $r=0.10-0.29$  ( $-0.10$  to  $-0.29$ ), negligible correlation;  $r=0.30-0.49$  ( $-0.30$  to  $-0.49$ ), low positive (negative) correlation;  $r=0.50-0.69$  ( $-0.50$  to  $-0.69$ ), moderate positive (negative) correlation;  $r=0.70-0.89$  ( $-0.70$  to  $-0.89$ ), high positive (negative) correlation;  $r=0.90-1.00$  ( $-0.90$  to  $-1.00$ ), very high positive (negative) correlation.[27] Spearman's correlation coefficients equal to 0.70 or over are desirable. To determine **criterion validity**, Spearman's correlation coefficient will be used. Concerning the effectiveness diagnostic test, receiver operating characteristic (**ROC**) curve analysis will be performed. The interpretation of the **AUC** as follows: fail ( $0.5 \leq \text{AUC} < 0.6$ ), poor ( $0.6 \leq \text{AUC} < 0.7$ ), fair ( $0.7 \leq \text{AUC} < 0.8$ ), good ( $0.8 \leq \text{AUC} < 0.9$ ), excellent ( $0.9 \leq \text{AUC}$ ). **Youden's Index** will be used to calculate the optimal cut-off value. Concerning the CFA,  $\chi^2/\text{df}$  for value lower than 5 the fit is acceptable. RMR and SRMR: the lower the values, the better the fit. GFI and CFI values over 0.90 are considered a good fit (with a maximum value equal to 1). Reference value for the RMSEA between 0.05 to 0.08 mean the adjustment is good. Factor loading values above or close to 0.70 are better to explain the structure. As for the clinical feasibility, the P-CIN will be considered a practical tool for implementation in clinical practice settings if 80% or more of the children completed the questionnaire independently.

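### The feasibility item asks about help with the survey, while feasibility is defined for the P-CIN alone; the item should name the P-CIN

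*Protocol*

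**What the plan says.** Under Feasibility, the protocol first defines the outcome: "Feasibility means percentage of children who completed the P-CIN independently". The next sentence gives the single item used to measure it: "Did the children need assistance by a parent or other adults to complete the survey". The definition names one instrument and the item does not.

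The decision rule is under Data analysis. The P-CIN is to be called practical for clinical use "if 80% or more of the children completed the questionnaire independently".

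The P-CIN is not the only form that participants answer. Its own section states "The P-CIN comprises 13 items". Validity assessment adds two scales for convergent validity: the Wong-Baker FACES rating and the PedsQL Cancer Module, of which the protocol says "This scale contains 27 items grouping into eight subscales".

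Data collection describes a single completion step after consent, in which "each child will be asked to complete the questionnaire independently". The sentence that follows, beginning "For those children who are unable to self-report, parents will", provides for parental help. It does not say with which form.

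**The concern.** The quantity defined and the question asked match only if respondents take the survey to mean the P-CIN. The protocol does not define the term, say when the item is asked, or provide for recording help separately for each instrument. A family that has just filled in three scales could reasonably answer for all of them. A child who managed the P-CIN alone but needed help with the PedsQL could then be counted as not having completed the P-CIN independently.

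What is at stake is the 80% verdict on practicality. Self-completion, or completion with a parent's help, is one of the reasons the background gives for choosing the P-CIN, so the percentage will be read with interest. One answer covering all forms cannot be split by instrument afterwards, so no analysis can repair it.

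**Working it through.** **Nothing to reproduce.** The 80% rule is a fixed threshold with no derivation, error rate or power. The calculation below only shows how sensitive the rule is to the wider reading of the item.

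**Inputs from the protocol**
- Planned number of children: 300 (Sample size: "We therefore determined to recruit 300 pediatric oncology patients in our validation study").
- Threshold: 80%, which is 0.80 × 300 = 240 children if all are evaluable.

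**Inputs not in the protocol (assumptions)**
- p, the true share completing the P-CIN alone: 85% to 95%.
- q, the share of those children who need help only with another form: 0 to 15%.

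**Formulas.** If the item is read as covering every form:
- measured rate = p × (1 − q), which can never exceed p;
- the measured rate equals 80% when q = 1 − 0.80/p;
- chance of meeting the rule = P(X ≥ 240), with X binomial(300, p(1 − q)).

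**Value of q that brings the measured rate down to 80%**
- p = 0.85: 1 − 0.80/0.85 = 5.9%, or 300 × (0.85 − 0.80) = 15 children.
- p = 0.90: 1 − 0.80/0.90 = 11.1%, or 30 children.
- p = 0.95: 1 − 0.80/0.95 = 15.8%, or 45 children.

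**Measured rate, with the chance of meeting the rule in brackets**

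| p | q = 0 | q = 5% | q = 10% | q = 15% |
|---|---|---|---|---|
| 0.85 | 85.0% (0.992) | 80.8% (0.661) | 76.5% (0.085) | 72.3% (0.001) |
| 0.90 | 90.0% (1.000) | 85.5% (0.996) | 81.0% (0.701) | 76.5% (0.085) |
| 0.95 | 95.0% (1.000) | 90.3% (1.000) | 85.5% (0.996) | 80.8% (0.661) |

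The q = 0 column is what an item confined to the P-CIN would give. The other columns apply only if respondents answer for all forms.

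**The case against.** The best defence is context. The item follows directly on a definition that names the P-CIN and is introduced as the means of evaluating that quantity. In the 80% rule the P-CIN is the subject of the sentence, so the questionnaire there naturally means the P-CIN. The intended quantity is therefore clear. This stands as to what the authors mean. It does not settle how a child, parent or nurse reads an item that leaves the instrument unnamed.

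Several stronger readings are tempting, and the protocol does not support them.

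- *A child helped only with the PedsQL must be recorded as needing help.* That follows only if the item comes after all the forms and is understood to cover them. The protocol states neither, nor does it say outright that all forms are completed in one sitting.
- *The P-CIN is only 13 of about 41 items (13 + 1 + 27), so most help will be needed elsewhere.* Item counts do not show where help is needed. Four P-CIN items are asked only if symptoms are reported, and five rate functional tasks. Children who need help may well need it with the P-CIN too, which would make q small.
- *The distortion is largest in the youngest children.* The PedsQL is the longest scale at every age, and children aged 5 to 7 have their own version with a simpler three-point response. The protocol gives no basis for an age gradient.
- *The 80% verdict will be wrong.* This needs both the wider reading and a true rate not far above 80%. At p = 0.90 and q = 5% the rule is still met with probability 0.996.

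It is also fair that feasibility is one descriptive percentage. The reliability, validity and factor results do not depend on it.

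**Conclusion.** The point holds as a wording mismatch with a possible one-way effect. The definition concerns the P-CIN, and the only measuring item does not say so. If respondents answer for every form, help needed only elsewhere can lower the P-CIN's percentage and cannot raise it.

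The size cannot be taken from the protocol. Under the assumed rates, a true 85% is pulled down to 80% by about 6% of the independent children needing help only elsewhere, a true 90% by about 11%, and a true 95% by about 16%. All of this assumes 300 evaluable children and the wider reading of the item. If respondents take it to mean the P-CIN, the effect is nil. The point is minor, but the protocol itself fixes the item's wording, and the ambiguity is easily removed before the question is put.

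**What to change.** Reword the item to: *Did the child need help from a parent or other adult to complete the P-CIN?* Place it directly after the P-CIN items, and base the 80% rule on that answer alone.

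A fixed order for all the forms is not needed. Replacing the word questionnaire with P-CIN in the 80% rule would be a helpful clarification and no more.

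The cost is one reworded item and its position on the form, with no additional data to collect. If the authors already mean the P-CIN, the change only makes the item say so.
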